7.6.4 Follow-up of laboratory abnormalities

If an unexplained laboratory test abnormality occurs and is clinically relevant, the test should be reperformed immediately and followed up until the test value returns to the normal range or a reasonable explanation for the abnormality is found. If there is a clear explanation, it should be recorded on the CRF.

7.6.5. Pregnancy reporting

Pregnancy should be strictly avoided during the study. If a female subject becomes pregnant during the study, the study treatment must be discontinued immediately and the investigator must be notified immediately. Pregnancy occurring within 6 months after completion of study treatment must also be reported to the investigator.

All male participants must use effective contraception throughout the study and for 6 months after the study ends. If a male patient's partner becomes pregnant during the study or within 6 months after the treatment ends, they should report this to the investigator and the sponsor. The investigator must report all pregnancy cases to the sponsor within 24 hours using the Clinical Trial Pregnancy Report Form.

Pregnancy events should be followed up until 30 days after the end of pregnancy. Pregnancy events include spontaneous or induced abortion, delivery details, birth defects or congenital malformations of the newborn, deformities and abnormalities of stillbirths, and complications of the mother and newborn. The time of reporting and visit should be referred to serious adverse events.

The investigator should advise the patient of the risks and possible effects on the fetus of continuing the pregnancy and should continue to monitor the patient until the end of the pregnancy. Information on the outcome of the pregnancy must be provided to the sponsor.

8. Safety evaluation

8.1 Analysis of population

- Informed Consent Set ICS: This analysis set will include all subjects who have signed an informed consent form.
- Intention-to-treat (ITT) analysis set: According to the principle of intention-to-treat analysis, all patients who were randomly assigned to the group at the time of randomization were analyzed according to the group into which they were assigned. This analysis set is the main analysis set for

efficacy endpoints.

- The Full Analysis Set (FAS) is defined as the group of all participants who were enrolled and received at least one dose of the study drug, following the intention to treat (ITT) principle. In analyses based on the FAS, participants are included according to their assigned group at enrollment, regardless of the actual treatment they received;
- In line with the protocol analysis set (Per-Protocol Set, PPS), ITT patients who did not experience significant protocol deviations that affected the efficacy assessment were included. The PP population was used for sensitivity analysis of the primary and key secondary efficacy endpoints.
- Safety set (Safety Set, SS): Will include all subjects who have received at least one study drug treatment. The safety set is the primary population for safety analysis.

8.2 General analysis

The mean, standard deviation, median, maximum and minimum values were used to summarize the measurement data; the frequency and percentage were used to summarize the count data; Kaplan-Meier survival rate was used to estimate the survival rate and draw the survival curve for time-event data, and the overall 95% confidence interval of median time was estimated when necessary.

8.3 Efficacy analysis and statistical methods

For the proportion of patients in each treatment group who achieved tumor downstaging (ypTNM 0-I stage), the proportion of participants with pathological complete remission, and the tumor regression grading (TRG), statistical analysis was conducted using mean values and standard deviations. For the three-year disease-free survival rate and overall survival time, Kaplan-Meier curves were plotted, and the 95% confidence interval for the median time was calculated using the Brookmeyer Crowley method. The Log-rank test was used to compare differences between groups, and the hazard ratios (HR) for each endpoint were

estimated using the Cox proportional hazards model, exploring the impact of factors other than treatment on these endpoints. Additionally, the number and percentage of cases that occurred at each endpoint, as well as the number and percentage of censored cases, were calculated and categorized by censoring reason.

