2.2 Research purpose

Main research objectives:

To evaluate the proportion of patients achieving tumor downstaging (ypTNM 0-I stage) in YWHAB high-expressing locally advanced rectal cancer treated with mFOLFOX6 combined with Citrus Flavonoid Tablets (Aimalang) as a neoadjuvant therapy, to provide evidence that Citrus Flavonoid Tablets (Aimalang) enhances the effectiveness of the mFOLFOX6 regimen in this patient population.

Secondary study objectives:

Efficacy evaluation: The proportion of pathological complete remission, 3-year disease-free survival (DFS), overall survival time (OS) and tumor regression grade TRG were evaluated in patients with YWHAB high expression locally advanced rectal cancer treated with mFOLFOX6 combined with citrus flavonoid tablets (Aimalang) as neoadjuvant therapy.

Safety evaluation: The treatment-related adverse reaction rate (grade 3 or above) of mFOLFOX6 combined with citrus flavonoid tablets (Aimalang) regimen for neoadjuvant treatment of YWHAB high expression local advanced rectal cancer patients was evaluated.

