4.1 Study treatment grouping

This study is a prospective, open-label, double-arm, Phase II clinical trial that includes a neoadjuvant treatment group using the mFOLFOX6 regimen and a neoadjuvant treatment group combining the mFOLFOX6 regimen with Citrus Flavonoid Tablets (Aimalang). The study aims to enroll patients with locally advanced rectal cancer who are in clinical stage I, II, or III. Endoscopic biopsy specimens will be collected for YWHAB immunohistochemical testing to identify patients with high YWHAB expression in locally advanced rectal cancer. These patients will then be randomly assigned to either the mFOLFOX6 treatment group or the mFOLFOX6 combined with Citrus Flavonoid Tablets (Aimalang) treatment group for neoadjuvant therapy. The mFOLFOX6 regimen involves 4-6 cycles before surgery and 6-8 cycles after surgery, with each cycle lasting 14 days: on day 1, 85 mg/m² of oxaliplatin is administered intravenously over 180 minutes; on day 1, 400 mg/m² of leucovorin is administered intravenously over 120 minutes; and on day 1, 2400 mg/m² of 5-fluorouracil is administered continuously intravenously for 46 hours. The Citrus Flavonoid Tablets (Aimalang) treatment regimen involves taking 500mg of Citrus Flavonoid Tablets (Aimalang) orally three times daily, with doses given on days 1-14 of each 14-day cycle.

This trial allows for dose adjustments. Patients who experience disease progression during neoadjuvant therapy may stop the study treatment and directly undergo surgery or follow local guidelines. If a patient cannot tolerate the planned 6 cycles of neoadjuvant therapy, early surgery can be considered. Any patient who has received another anticancer regimen before surgery will stop the study treatment and be managed according to local guidelines. The postoperative

treatment for both groups is determined by the investigator, which may include continuing the mFOLFOX6 regimen combined with Citrus Flavonoid Tablets (Aimalang). It is important to note that all patients in the control group are prohibited from taking Citrus Flavonoid Tablets (Aimalang) without authorization during the trial. If a patient needs to take this medication for any reason, they should consult their primary physician, who will decide whether to use an alternative or discontinue the patient's participation in the trial.

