8.5 Sample size determination

This study primarily focuses on the rate of tumor downstaging (ypTNM 0-I stage) in each treatment group. Based on current data, after

neoadjuvant chemotherapy with mFOLFOX6, approximately 35% of locally advanced rectal cancer patients achieve tumor downstaging (ypTNM 0-I stage). Among these, about one-third (n=90) of YWHAB high-expressing locally advanced rectal cancer patients achieved a tumor downstaging rate of about 25%, while about two-thirds (n=90) of YWHAB low-expressing locally advanced rectal cancer patients achieved a tumor downstaging rate of about 43%. It is estimated that the tumor downstaging rate for YWHAB high-expressing patients receiving mFOLFOX6 combined with citrus flavonoid tablets (Aimalang) neoadjuvant chemotherapy is 40%, with a significance level of 0.05, an efficiency of 0.8, and a dropout rate of 10%. The sample size was estimated to be 236 using PASS V15 software.

Ethical considerations

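### Section 8.3 prespecifies no between-arm comparison for the primary endpoint: no test, sidedness, effect measure or confidence interval for downstaging

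*Combined protocol and SAP*

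**What the plan says.** Section 8.3 groups downstaging, pathological complete remission (pCR) and tumor regression grade (TRG) in one sentence. The whole analysis it gives them is that "statistical analysis was conducted using mean values and standard deviations". It then turns to 3-year DFS and OS, with Kaplan-Meier curves, confidence intervals for the median, "The Log-rank test was used to compare differences between groups" and Cox hazard ratios. It closes by asking for "the number and percentage of cases that occurred at each endpoint" together with the censored cases.

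Other sections bear on the point:

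- Section 2.2 gives a comparative objective: "to provide evidence that Citrus Flavonoid Tablets (Aimalang) enhances the effectiveness of the mFOLFOX6 regimen in this patient population".
- Section 4.1 randomises: "These patients will then be randomly assigned to either the mFOLFOX6 treatment group or the mFOLFOX6 combined with Citrus Flavonoid Tablets (Aimalang) treatment group". No allocation ratio is given.
- Section 6.2 keeps patients who do not meet the primary endpoint in the denominator.
- Section 8.1 says of the ITT set: "This analysis set is the main analysis set for" the efficacy endpoints.
- Section 8.2 sets the general rule that "the frequency and percentage were used to summarize the count data", and keeps means and standard deviations for measurement data.
- Section 8.5 sizes the trial on 25% versus 40%, "with a significance level of 0.05, an efficiency of 0.8, and a dropout rate of 10" percent. It names neither a test nor a sidedness.
- Section 8.4 defers detail to a statistical analysis plan, but for safety only.

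**The concern.** The plan names a between-group test for time-to-event secondary endpoints and none for the primary endpoint. A significance level and a power have meaning only in relation to a test, so a comparison is clearly intended; it is just not specified. The trial is open-label. If the test and its sidedness stay open until results are known, the same data can be called a success or a failure by a choice the plan does not constrain. Section 8.5 also has no stated analysis that its power could refer to.

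The mean and standard deviation wording is a lesser matter. It contradicts 8.2, and for TRG it treats four ordered grades as a measured scale.

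**Working it through.** **Inputs.** From 8.5: control rate 0.25, combination rate 0.40, significance level 0.05, power 0.8, dropout 10%, total 236. Assumed, because not stated: 1:1 allocation, so 236/2 = 118 per arm.

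**1. Does 236 reveal the intended test?** Unpooled two-proportion formula: n per arm = (z_α + z_β)² × [p₁(1−p₁) + p₂(1−p₂)] / (p₂−p₁)², where (0.1875 + 0.24)/0.0225 = 19.

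- One-sided: (1.645 + 0.842)² × 19 = 117.5, so 118 per arm and 236 in total before dropout; 264 after dividing by 0.9.
- Two-sided: (1.960 + 0.842)² × 19 = 149.1, so 150 per arm and 300 in total before dropout; 334 after.
- Pooled formula: 240 one-sided and 304 two-sided before dropout; 268 and 338 after.

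The figure 236 is matched exactly only by a one-sided unpooled calculation with no dropout allowance. None of the variants tried that uses all the stated inputs gives 236, so 8.5 does not settle the sidedness.

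**2. How often would sidedness decide the verdict?** Exact binomial enumeration of the pooled z test, z = (p̂₂ − p̂₁)/√[p̄(1−p̄)(1/n₁ + 1/n₂)], without continuity correction; success means rejection in favour of the combination.

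| Scenario (control/combination) | z > 1.645 | z > 1.960 | Difference |
|---|---|---|---|
| 25% vs 40%, 118/118 | 0.800 | 0.696 | 0.103 |
| 25% vs 40%, 79/157 | 0.754 | 0.634 | 0.120 |
| 25% vs 40%, 157/79 | 0.760 | 0.654 | 0.106 |
| 25% vs 25%, 118/118 | 0.050 | 0.025 | 0.025 |

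**3. Boundary illustrations, chosen to show the mechanism.**

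- 30/118 (25.4%) vs 42/118 (35.6%): p̄ = 72/236 = 0.305, SE = 0.0599, z = 0.1017/0.0599 = 1.696. The p-value is 0.045 one-sided and 0.090 two-sided. Newcombe 95% CI: −1.6 to 21.5 points.
- 30/118 vs 44/118 (37.3%): z = 1.964. The two-sided p-value is 0.049 uncorrected, 0.068 with Yates' correction and 0.068 by Fisher's exact test. Newcombe 95% CI: 0.02 to 23.3 points, which agrees with the uncorrected test.

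**4. Power to be restated once a test is named** (pooled z test, no continuity correction).

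| Basis | One-sided | Two-sided |
|---|---|---|
| 118 per arm, all evaluable | about 80% | about 70% |
| 106 per arm (118 × 0.9) | about 76% | about 65% |
| 118 per arm, dropouts counted as not downstaged (0.25 × 0.9 = 22.5% vs 0.40 × 0.9 = 36%) | about 74% | about 63% |

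**5. Mean and standard deviation.** For a yes/no outcome the mean is the proportion and the SD is √[p(1−p)]: 0.433 at 25% and 0.490 at 40%. The SD adds nothing, but nothing is lost either. For TRG, take a constructed example with 10/40/40/10% and 20/10/70/0% in grades 0/1/2/3. Both means are 1.5 (0.40 + 0.80 + 0.30; 0.10 + 1.40 + 0). Both second moments are 2.9, so both SDs are √(2.9 − 2.25) = 0.81. Yet TRG 0 is 10% vs 20%, and TRG 0–1 is 50% vs 30%.

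**The case against.** The strongest reply is that much is already fixed: the ITT set, the denominator rule and the 0.05 level. Arm proportions and arm sizes determine the difference and any standard test, so the trial could still answer its question. This is right as far as it goes. A reader might infer that the data could never yield a comparison, and the documents do not support that. What is missing is prespecification of the test, its sidedness and the effect estimate.

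The closing sentence of 8.3 on numbers and percentages might be thought to fill the gap. It follows the time-to-event text and is tied to censoring. Even if it covers downstaging, it describes the arms and does not compare them.

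A reader might also infer that means and standard deviations make the primary summary wrong. They do not: for downstaging and pCR this is wording, and 8.2 already gives the right summary. The TRG example was constructed to make the point; it supports reporting the grade distribution, not a particular test, and TRG is a secondary endpoint.

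Finally, it is tempting to say the plan must be two-sided. Nothing in the documents says so. The objective is directional, and the only exact match to 236 is one-sided. The p-value contrasts in step 3 are boundary cases; the 10% figure is the more representative one.

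**Conclusion.** The gap is real and should be closed before outcome data are reviewed. Section 8.3 states an analysis for the primary endpoint that cannot by itself deliver the comparison that 2.2 and 8.5 require, and no other section supplies it. Under 1:1 allocation and 25% versus 40%, the unstated sidedness alone changes the verdict in about 10% of trials (11% to 12% under 2:1 allocation in either direction). With no true effect and 25% in both arms, it doubles the chance of wrongly declaring success for the combination, from 2.5% to 5.0%. These sizes rest on the assumed allocation, the planning rates and an uncorrected pooled test. The conflict with 8.2 is secondary: editorial for the yes/no endpoints, and a reporting change for TRG. A reader might infer from the power figures that enrolment must rise. This point does not require that, and how 236 was derived is a separate matter.

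**What to change.** Replace the first sentence of 8.3 with text such as:

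> *Primary analysis (ITT, denominator rule of 6.2): number and percentage downstaged by arm; difference in proportions (combination minus control) with a 95% CI (e.g. Newcombe); Pearson chi-square (two-proportion z) test without continuity correction at 0.05, [one-sided / two-sided, to be stated by the sponsor]. pCR: same method, as a secondary endpoint. TRG: number and percentage in each grade by arm.*

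The sponsor should state in both 8.3 and 8.5, before outcome data are reviewed, whether the test is one- or two-sided and which exact variant is used. Another named test or interval would serve equally well if it is fixed in advance. Section 8.5 should restate power to match.

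The cost is a wording amendment with no new data, but the stated power will fall. The restated figures run from about 80% (one-sided, all 118 per arm evaluable) down to about 63% (two-sided, with the 10% dropouts counted as not downstaged). The sponsor must then either accept and report that power or take up the sample size as its own question; this change does not itself call for more patients.

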8.4 Safety analysis and statistical methods

The security analysis will be based on the security set. The security analysis is limited to descriptive statistical summaries, including but not limited to the following aspects, which will be described in the statistical analysis plan:

- Summary of adverse events (all-cause and treatment-related);
- Incidence and severity of adverse events (all-cause and treatment-related);
- Summary of details of serious adverse events;
- Analysis of adverse event correlation;
- Abnormal occurrence of laboratory indicators, vital signs and electrocardiogram data.

The security analysis will be based on descriptive statistical summaries and based on the security set.

This study will use the standard medical terminology set (MedDRA) of pharmaceutical management to code adverse events. The study will use tables to list all adverse events, drug-related adverse events, serious adverse events, and drug-related serious adverse events that occurred during treatment, according to the NCI CTCAE version 6.0 standard and using the worst grading. Additionally, the study will summarize the laboratory test parameters during the research period according to the NCI CTCAE version 6.0 standard and using the worst grading.

8.5 Sample size determination

This study primarily focuses on the rate of tumor downstaging (ypTNM 0-I stage) in each treatment group. Based on current data, after

neoadjuvant chemotherapy with mFOLFOX6, approximately 35% of locally advanced rectal cancer patients achieve tumor downstaging (ypTNM 0-I stage). Among these, about one-third (n=90) of YWHAB high-expressing locally advanced rectal cancer patients achieved a tumor downstaging rate of about 25%, while about two-thirds (n=90) of YWHAB low-expressing locally advanced rectal cancer patients achieved a tumor downstaging rate of about 43%. It is estimated that the tumor downstaging rate for YWHAB high-expressing patients receiving mFOLFOX6 combined with citrus flavonoid tablets (Aimalang) neoadjuvant chemotherapy is 40%, with a significance level of 0.05, an efficiency of 0.8, and a dropout rate of 10%. The sample size was estimated to be 236 using PASS V15 software.

Ethical considerations

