Currently, the multimodal treatment for stage II or III rectal cancer typically includes preoperative chemoradiotherapy with fluorouracil-based regimens, total mesorectal excision (TME), and postoperative adjuvant chemotherapy[7-8]. The FOWARC study conducted by our center has demonstrated that, compared to standard preoperative chemoradiotherapy, patients who received mFOLFOX6 neoadjuvant chemotherapy showed no significant differences in tumor downstaging, disease-free survival (DFS), local recurrence rate, or overall

survival. However, the incidence of postoperative anastomotic leakage was significantly lower in patients receiving only mFOLFOX6 neoadjuvant chemotherapy, with better anal function and improved long-term quality of life. This suggests that mFOLFOX6 neoadjuvant chemotherapy can partially replace preoperative chemoradiotherapy, effectively avoiding radiotherapy-related side effects without compromising treatment efficacy. The findings have been cited in the NCCN international guidelines[9-11]. Studies have shown that tumor downstaging (ypTNM 0-I stage) is significantly associated with better DFS in locally advanced rectal cancer patients who receive neoadjuvant therapy[9-11]. The FOWARC study found that about 35% of locally advanced rectal cancer patients who received mFOLFOX6 neoadjuvant chemotherapy had tumor downstaging. This indicates that some patients may be less sensitive to mFOLFOX6 neoadjuvant chemotherapy. Identifying and screening out these patients who are resistant to mFOLFOX6 treatment, and further improving their tumor downstaging rate and prognosis through mFOLFOX6 chemotherapy combined with targeted therapy, holds promise.

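### Section 8.5 gives 90 patients to both a one-third and a two-thirds subgroup, leaves its 25% control rate unsourced, and states a sample of 236 that falls short of 80% power once its own 10% dropout is applied

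*Combined protocol and SAP*

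**What the plan says.** All planning inputs stand in section 8.5 (Sample size determination).

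- Overall: on mFOLFOX6, "approximately 35% of locally advanced rectal cancer patients achieve tumor downstaging". The background section gives the same figure and attributes it to the centre's earlier randomised study: "about 35% of locally advanced rectal cancer patients who received mFOLFOX6 neoadjuvant chemotherapy had tumor downstaging".
- High expressers: "about one-third (n=90) of YWHAB high-expressing locally advanced rectal cancer patients achieved a tumor downstaging rate of about 25" per cent.
- Low expressers: "about two-thirds (n=90) of YWHAB low-expressing" patients, with a rate of about 43%.
- Design: 40% expected on the combination, significance level 0.05, power 0.8, dropout 10%, and a total of 236 from PASS V15.

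The section does not state the test, whether it is one- or two-sided, the allocation ratio, or whether 236 is before or after the dropout allowance. Neither subgroup rate comes with an event count or a citation.

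**The concern.** The same count is attached to two shares that differ by a factor of two. Nothing in the text explains this, for example separate cohorts or a sampled subset of low expressers. The sentence matters because it is the only place where the documents give the 25% control rate. A reader who wants to judge that rate finds no numerator, no source, and a denominator whose description conflicts with the line beside it.

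The same paragraph then states a total that cannot be traced to its own inputs. If 236 is short, the trial may be too small to detect the improvement from 25% to 40% that it was designed around.

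**Working it through.** **1. Counts and shares.** If 90 is one-third, the cohort is 270 and the other two-thirds is 180. If 90 is two-thirds, the cohort is 135 and the other third is 45. If both groups are 90, each is one-half. The printed text fits none of these.

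**2. Implied overall rate.**
- Equal counts: (90 × 25% + 90 × 43%) / 180 = 34.0%, or 33.5% to 34.5% allowing for rounding of the two rates.
- Stated shares: 25%/3 + 43% × 2/3 = 37.0%, or 36.5% to 37.5%.
- Exactly 35% would need a high-expression share of (43 − 35)/(43 − 25) = 44%.

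**3. Reproducing 236.** Inputs: p1 = 0.25, p2 = 0.40, difference 0.15, alpha 0.05, power 0.80 (z = 0.842). I assume 1:1 allocation and try both sidednesses (z = 1.645 or 1.960). The pooled term is 2 × 0.325 × 0.675 = 0.43875. The unpooled term is 0.25 × 0.75 + 0.40 × 0.60 = 0.4275.

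Pooled, per arm: n = (z_alpha √0.43875 + 0.842 √0.4275)² / 0.15². Unpooled, per arm: n = (z_alpha + 0.842)² × 0.4275 / 0.15². Dropout is applied as total/(1 − 0.10).

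| Calculation | Per arm | Total | Total with 10% dropout |
|---|---|---|---|
| One-sided, unpooled | 117.5, so 118 | 236 | 263 |
| One-sided, pooled | 119.5, so 120 | 240 | 267 |
| Two-sided, unpooled | 149.1, so 150 | 300 | 334 |
| Two-sided, pooled | 151.9, so 152 | 304 | 338 |

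Continuity-corrected and arcsine versions were also run. The only exact match to 236 is the one-sided unpooled total before dropout. No version that includes the 10% gives 236.

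**4. Power of 236.** Pooled test: power = Φ[(0.15 − z_alpha √(0.43875/n)) / √(0.4275/n)].
- All evaluable, n = 118 per arm: 69% two-sided, 80% one-sided. Exact calculation gives 70% and 80%.
- After 10% loss, 236 × 0.9 = 212, so n = 106 per arm. Two-sided: (0.15 − 1.960 × 0.06434)/0.06351 = 0.376, power 65%. One-sided: (0.15 − 1.645 × 0.06434)/0.06351 = 0.696, power 76%.

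**5. How firm the 25% is.** If 90 is the right denominator, about 25% means 22 or 23 events. The Wilson 95% intervals are about 17% to 34% and 18% to 35%.

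**6. Sensitivity to the control rate.** Two-sided, pooled, 40% on the combination, 10% dropout: the total is 229 at a control rate of 22%, 338 at 25% and 543 at 28%. One-sided, the totals are 180, 267 and 427.

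**The case against.** The strongest reply is that the slip is clerical. The 25% is stated directly as the high-expresser rate. The low-expresser count, the 43% and the overall 35% are not inputs to a 25% versus 40% calculation. If the low-expresser count is the misprint, nothing in the calculation changes. If the high-expresser count is the misprint, the precision of the 25% changes but not the stated rate. This stands.

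A reader might infer that the planning rates contradict the overall 35%. The documents do not support that. Every rate is given as approximate, and the printed counts give 34%. Only the printed shares give 37%. It is also not established that the patients typed for YWHAB are the whole cohort behind the 35%.

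A reader might also solve for a different high-expresser rate by holding 35% and 43% fixed. That treats two rounded figures as exact and discards the one rate that the plan actually uses. With a one-third share it multiplies any error in the overall rate by three. With equal counts, an overall rate of 34% returns 2 × 34 − 43 = 25% exactly. Nor can the disputed share be turned into a screening shortfall: the documents set no screening target, and other eligibility criteria also apply.

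On power, it can be said that section 8.1 makes intention-to-treat the main efficacy set, so all 236 stay in the denominator. That does not restore 80%. Suppose that 10% in each arm have no pathology result and count as not downstaged. The rates become 0.9 × 25% = 22.5% and 0.9 × 40% = 36%, and the same pooled formula at 118 per arm (mean rate 29.25%) gives about 63% two-sided or 74% one-sided.

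**Conclusion.** The point holds in a limited form. At least one count or share in section 8.5 is wrong. The documents do not show that the 25% control rate is wrong, only that it cannot be checked and that the sample size depends heavily on it.

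The finding with consequences for the design is that the stated 0.8 power is not delivered under the section's own inputs. With 236 randomised and 10% lost, power is about 65% two-sided or 76% one-sided. The 80% is reached only with a one-sided 0.05 test and no dropout. This rests on 1:1 allocation, which is not stated, and on a normal-approximation comparison of two proportions. Because sidedness is not stated either, both values are shown. A correction is warranted before the sample size is relied on, but the duplicated count alone would be close to editorial.

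**What to change.** In section 8.5:

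1. Correct the two counts or the two shares from the source data.
2. Give events over denominators for high expressers, low expressers and the overall group. Name the source, and say whether all three come from the same patients.
3. State the test, its sidedness, the allocation ratio, and whether 236 is before or after dropout. State also how patients without a pathology result enter the primary analysis.
4. Restate the power of 236 on that basis, or revise the total. If 25% versus 40% is kept, 80% power after 10% dropout needs 263 to 267 one-sided, or 334 to 338 two-sided, by the formulas above.

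The cost is one check of existing data, one rerun of the software and a text amendment. The drawback is that the stated power becomes less favourable, or the sample size rises.
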